12.2 Disease Parameters

Measurable disease: Measurable lesions are defined as those that can be accurately measured in at least one dimension (longest diameter to be recorded) as >20 mm by chest x-ray, as >10 mm with CT scan, or >10 mm with calipers by clinical exam. All tumor measurements must be recorded in millimeters (or decimal fractions of centimeters).

Malignant lymph nodes: To be considered pathologically enlarged and measurable, a lymph node must be >15 mm in short axis when assessed by CT scan (CT scan slice thickness recommended to be no greater than 5 mm). At baseline and in follow-up, only the short axis will be measured and followed.

Non-measurable disease: All other lesions (or sites of disease), including small lesions (longest diameter <10 mm or pathological lymph nodes with ≥ 10 to <15 mm short axis), are considered non-measurable disease. Bone lesions, leptomeningeal disease, ascites, pleural/pericardial effusions, lymphangitis cutis/pulmonitis, inflammatory breast disease, and abdominal masses (not followed by CT or MRI), are considered as non-measurable.

Note: Cystic lesions that meet the criteria for radiographically defined simple cysts should not be considered as malignant lesions (neither measurable nor non-measurable) since they are, by definition, simple cysts.

‘Cystic lesions’ thought to represent cystic metastases can be considered as measurable lesions, if they meet the definition of measurability described above. However, if non-cystic lesions are present in the same patient, these are preferred for selection as target lesions.

Target lesions: All measurable lesions up to a maximum of 2 lesions per organ and 5 lesions in total, representative of all involved organs, should be identified as target lesions and recorded and measured at baseline. Target lesions should be selected on the basis of their size (lesions with the longest diameter), be representative of all involved organs, but in addition should be those that lend themselves to reproducible repeated measurements. It may be the case that, on occasion, the largest lesion does not lend itself to reproducible measurement in which circumstance the next largest lesion which can be measured reproducibly should be selected. A sum of the diameters (longest for non-nodal lesions, short axis for nodal lesions) for all target lesions will be calculated and reported as the baseline sum diameters. If lymph nodes are to be included in the sum, then only the short axis is added into the sum. The baseline sum diameters will be used as reference to further characterize any objective tumor regression in the measurable dimension of the disease.

Non-target lesions: All other lesions (or sites of disease) including any measurable lesions over and above the 5 target lesions should be identified as non-target lesions and should also be recorded at baseline. Measurements of these lesions are not required, but the presence, absence, or in rare cases unequivocal progression of each should be noted throughout follow-up.

12.3 Methods for Evaluation of Measurable Disease

All measurements should be taken and recorded in metric notation using a ruler or calipers. All baseline evaluations should be performed as closely as possible to the beginning of treatment and never more than 4 weeks before the beginning of the treatment.

The same method of assessment and the same technique should be used to characterize each identified and reported lesion at baseline and during follow-up. Imaging-based evaluation is preferred to evaluation by clinical examination unless the lesion(s) being followed cannot be imaged but are assessable by clinical exam.

Clinical lesions: Clinical lesions will only be considered measurable when they are superficial (e.g., skin nodules and palpable lymph nodes) and ≥ 10 mm diameter as assessed using calipers (e.g., skin nodules). In the case of skin lesions, documentation by color photography, including a ruler to estimate the size of the lesion, is recommended.

Chest x-ray: Lesions on chest x-ray are acceptable as measurable lesions when they are clearly defined and surrounded by aerated lung. However, CT is preferable.

Conventional CT and MRI: This guideline has defined measurability of lesions on CT scan based on the assumption that CT slice thickness is 5 mm or less. If CT scans have slice thickness greater than 5 mm, the minimum size for a measurable lesion should be twice the slice thickness. MRI is also acceptable in certain situations (e.g. for body scans).

Use of MRI remains a complex issue. MRI has excellent contrast, spatial, and temporal resolution; however, there are many image acquisition variables involved in MRI, which greatly impact image quality, lesion conspicuity, and measurement. Furthermore, the availability of MRI is variable globally. As with CT, if an MRI is performed, the technical specifications of the scanning sequences used should be optimized for the evaluation of the type and site of disease. Furthermore, as with CT, the modality used at follow-up should be the same as was used at baseline and the lesions should be measured/assessed on the same pulse sequence. It is beyond the scope of the RECIST guidelines to prescribe specific MRI pulse sequence parameters for all scanners, body parts, and diseases. Ideally, the same type of scanner should be used and the image acquisition protocol should be followed as closely as possible to prior scans. Body scans should be performed with breath-hold scanning techniques, if possible.

PET-CT: At present, the low dose or attenuation correction CT portion of a combined PET-CT is not always of optimal diagnostic CT quality for use with RECIST measurements. However, if the site can document that the CT performed as part of a PET-CT is of identical diagnostic quality to a diagnostic CT (with IV and oral contrast), then the CT portion of the PET-CT can be used for RECIST measurements and can be used interchangeably with conventional CT in accurately measuring cancer lesions over time. Note, however, that the PET portion of the CT introduces additional data which may bias an investigator if it is not routinely or serially performed.

The cytological confirmation of the neoplastic origin of any effusion that appears or worsens during treatment when the measurable tumor has met criteria for response or stable disease is mandatory to differentiate between response or stable disease (an effusion may be a side effect of the treatment) and progressive disease.

FDG-PET: While FDG-PET response assessments need additional study, it is sometimes

reasonable to incorporate the use of FDG-PET scanning to complement CT scanning in assessment of progression (particularly possible 'new' disease). New lesions on the basis of FDG-PET imaging can be identified according to the following algorithm:

- Negative FDG-PET at baseline, with a positive FDG-PET at follow-up is a sign of PD based on a new lesion.
- No FDG-PET at baseline and a positive FDG-PET at follow-up: If the positive FDG-PET at follow-up corresponds to a new site of disease confirmed by CT, this is PD. If the positive FDG-PET at follow-up is not confirmed as a new site of disease on CT, additional follow-up CT scans are needed to determine if there is truly progression occurring at that site (if so, the date of PD will be the date of the initial abnormal FDG-PET scan). If the positive FDG-PET at follow-up corresponds to a pre-existing site of disease on CT that is not progressing on the basis of the anatomic images, this is not PD.
- FDG-PET may be used to upgrade a response to a CR in a manner similar to a biopsy in cases where a residual radiographic abnormality is thought to represent fibrosis or scarring. The use of FDG-PET in this circumstance should be prospectively described in the protocol and supported by disease-specific medical literature for the indication. However, it must be acknowledged that both approaches may lead to false positive CR due to limitations of FDG-PET and biopsy resolution/sensitivity.

Note: A 'positive' FDG-PET scan lesion means one which is FDG avid with an uptake greater than twice that of the surrounding tissue on the attenuation corrected image.

12.4 Response Criteria

12.4.1 Evaluation of Target Lesions

Complete Response (CR): Disappearance of all target lesions. Any pathological lymph nodes (whether target or non-target) must have reduction in short axis to <10 mm.

Partial Response (PR): At least a 30% decrease in the sum of the diameters of target lesions, taking as reference the baseline sum diameters.

Progressive Disease (PD): At least a 20% increase in the sum of the diameters of target lesions, taking as reference the smallest sum on study (this includes the baseline sum if that is the smallest on study). In addition to the relative increase of 20%, the sum must also demonstrate an absolute increase of at least 5 mm. (Note: the appearance of one or more new lesions is also considered progressions).

Stable Disease (SD): Neither sufficient shrinkage to qualify for PR nor sufficient increase to qualify for PD, taking as reference the smallest sum diameters while on study.

12.4.2 Evaluation of Non-Target Lesions

Complete Response (CR): Disappearance of all non-target lesions and normalization of tumor marker level. All lymph nodes must be non-pathological in size (<10 mm short axis).

Note: If tumor markers are initially above the upper normal limit, they must normalize for a patient to be considered in complete clinical response.

Non-CR/Non-PD: Persistence of one or more non-target lesion(s) and/or maintenance of tumor marker level above the normal limits.

Progressive Disease (PD): Appearance of one or more new lesions and/or unequivocal progression of existing non-target lesions. Unequivocal progression should not normally trump target lesion status. It must be representative of overall disease status change, not a single lesion increase.

Although a clear progression of “non-target” lesions only is exceptional, the opinion of the treating physician should prevail in such circumstances, and the progression status should be confirmed in 4-6 weeks by the Principal Investigator.

12.4.3 Evaluation of Best Overall Response

The best overall response is the best response recorded from the start of the treatment until disease progression/recurrence (taking as reference for progressive disease the smallest measurements recorded since the treatment started). The patient's best response assignment will depend on the achievement of both measurement and confirmation criteria.

For Patients with Measurable Disease (i.e., Target Disease)

Target Lesions	Non-Target Lesions	New Lesions	Overall Response	Best Overall Response when Confirmation is Required*
CR	CR	No	CR	>4 wks. Confirmation**
CR	Non-CR/Non-PD	No	PR	>4 wks. Confirmation**
CR	Not evaluated	No	PR	
PR	Non-CR/Non-PD/not evaluated	No	PR	
SD	Non-CR/Non-PD/not evaluated	No	SD	Documented at least once >4 wks. from baseline**
PD***	Any	Yes or No	PD	no prior SD, PR or CR
Any	PD****	Yes or No	PD	
Any	Any	Yes	PD	
* See RECIST 1.1 manuscript for further details on what is evidence of a new lesion.				
** Only for non-randomized trials with response as primary endpoint.				

*** If the patient is clinically stable, treatment may continue with repeated scans in 4 weeks to rule out pseudoprogression
 **** In exceptional circumstances, unequivocal progression in non-target lesions may be accepted as disease progression.
 Note: Patients with a global deterioration of health status requiring discontinuation of treatment without objective evidence of disease progression at that time should be reported as “symptomatic deterioration.” Every effort should be made to document the objective progression even after discontinuation of treatment.

For Patients with Non-Measurable Disease (i.e., Non-Target Disease)

Non-Target Lesions	New Lesions	Overall Response
CR	No	CR
Non-CR/non-PD	No	Non-CR/non-PD*
Not all evaluated	No	not evaluated
Unequivocal PD	Yes or No	PD
Any	Yes	PD
* ‘Non-CR/non-PD’ is preferred over ‘stable disease’ for non-target disease since SD is increasingly used as an endpoint for assessment of efficacy in some trials so to assign this category when no lesions can be measured is not advised		

12.4.4 Duration of Response

Duration of overall response: The duration of overall response is measured from the time measurement criteria are met for CR or PR (whichever is first recorded) until the first date that recurrent or progressive disease is objectively documented (taking as reference for progressive disease the smallest measurements recorded since the treatment started).

The duration of overall CR is measured from the time measurement criteria are first met for CR until the first date that progressive disease is objectively documented.

Duration of stable disease: Stable disease is measured from the start of the treatment until the criteria for progression are met, taking as reference the smallest measurements recorded since the treatment started, including the baseline measurements.

12.4.5 Progression-Free Survival

PFS is defined as the duration of time from start of treatment to time of progression or death, whichever occurs first.

12.4.6 Response Review

It is strongly recommended that all responses be reviewed by an expert(s) independent of the study at the study’s completion. Simultaneous review of the patients’ files and radiological images is the best approach.

13.0 DATA AND SAFETY MONITORING

In compliance with the Washington University Institutional Data and Safety Monitoring Plan, the Principal Investigator will provide a Data and Safety Monitoring (DSM) report to the Washington University Quality Assurance and Safety Monitoring Committee (QASMC) semi-annually beginning six months after accrual has opened (if at least one patient has been enrolled) or one year after accrual has opened (if no patients have been enrolled at the six-month mark).

The Principal Investigator will review all patient data at least every six months, and provide a semi-annual report to the QASMC. This report will include:

- HRPO protocol number, protocol title, Principal Investigator name, data coordinator name, regulatory coordinator name, and statistician
- Date of initial HRPO approval, date of most recent consent HRPO approval/revision, date of HRPO expiration, date of most recent QA audit, study status, and phase of study
- History of study including summary of substantive amendments; summary of accrual suspensions including start/stop dates and reason; and summary of protocol exceptions, error, or breach of confidentiality including start/stop dates and reason
- Study-wide target accrual and study-wide actual accrual
- Protocol activation date
- Average rate of accrual observed in year 1, year 2, and subsequent years
- Expected accrual end date
- Objectives of protocol with supporting data and list the number of participants who have met each objective
- Measures of efficacy
- Early stopping rules with supporting data and list the number of participants who have met the early stopping rules
- Power analysis and/or interim analysis (if described in the protocol)
- Summary of toxicities
- Abstract submissions/publications
- Summary of any recent literature that may affect the safety or ethics of the study

The study principal investigator and Research Patient Coordinator will monitor for serious toxicities on an ongoing basis. Once the principal investigator or Research Patient Coordinator becomes aware of an adverse event, the AE will be reported to the HRPO and QASMC according to institutional guidelines.

14.0 STATISTICAL CONSIDERATIONS

14.1 Objectives and Endpoints

The primary objective of this study is to determine the overall response rate (ORR) for the combination of ramucirumab and atezolizumab in patients with NSCLC who have previously received an ICB.

The secondary objectives include

- To determine the overall survival (OS) for the combination of ramucirumab and atezolizumab in patients with NSCLC who have previously received an ICB.
- To determine the progression-free survival (PFS) for the combination of ramucirumab and atezolizumab in patients with NSCLC who have previously received an ICB.
- To determine clinical benefit rate (CBR) for the combination of ramucirumab and atezolizumab in patients with NSCLC who have previously received an ICB. CBR is defined as the percentage of patients who have achieved responses or stable disease.
- To evaluate toxicity and tolerability of this combination as measured by NCI-CTCAE version 5.0.

The exploratory objectives include

- To explore the relationship of the immunophenotype of peripheral blood immune cells and response to combined therapy.
- To explore the changes in tumor immune cell infiltrate after treatment and relationship with response.

14.2 Study Design

This single institution study will be designed using Simon's two-stage MiniMax design. We plan to enroll twenty-one (21) advanced-stage NSCLC patients.

Assuming a null hypothesis of ORR less than 5% in this setting, we hypothesize that ORR of 20% or higher warrants further investigation. A total number of 21 patients allows an 80% power at 1-sided alpha of 0.1 to detect the expected difference. If 4 or more responders are observed at the end of the trial, we would conclude that there is preliminary evidence for efficacy warranting further investigation.

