1.6 Amendment #3 Study Continuation

1.6.1 Synopsis

The primary objective of the RamAtezo trial is to determine the overall response rate for the combination of ramucirumab and atezolizumab in patients with NSCLC previously treated with immune checkpoint blocker. This is an unmet need where there are few treatment options for patients after tumor progression on immune checkpoint blockers, particularly when used in combination with platinum-based doublet in the first-line setting.

The study design uses a Simon's two-stager MiniMax design where 12 patients are enrolled into the stage I. In case of one or more responses, the study will accrue 9 more patients, with a total of 4 responders indicating the preliminary evidence of efficacy.

Although there were no responses among the initial 12 patients, 8 patients had tumor reduction from baseline, including patient reaching 27% reduction, only 3% below the threshold for the RECIST criteria for response. Furthermore, the treatment has been well tolerated and 3 out of the 12 patients (25%) are still on treatment with progression-free survival higher than 6 months.

Therefore, we believe that the study should continue with the accrual of the additional 9 patients with the primary endpoint remaining the overall response rate. In this case, the Minimax design will be replaced by a simple enrollment of 21 patients.

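### Section 14.2 still describes a Simon two-stage MiniMax design that Amendment #3 replaced after 0/12 responses, and its 4-of-21 rule has 63% power, not 80%

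*Combined protocol and SAP*

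**What the plan says.** Section 14.2 names Simon's "two-stage MiniMax design. We plan to enroll twenty-one (21) advanced-stage NSCLC patients". It sets a null ORR below 5% against a target of 20% or higher and states: "A total number of 21 patients allows an 80% power at 1-sided alpha of 0.1 to detect the expected difference". Its success criterion is "If 4 or more responders are observed at the end of the trial". It gives no stage sizes and no continuation rule.

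Those details appear only in Section 1.6.1, the Amendment #3 synopsis. There the first stage is 12 patients, and the continuation rule reads: "In case of one or more responses, the study will accrue 9 more patients". The criterion for success at the end is given as "with a total of 4 responders indicating the preliminary evidence of efficacy". The section then reports the result: "Although there were no responses among the initial 12 patients". It argues for continuing because of tumor shrinkage, tolerability and the fact that "3 out of the 12 patients (25%) are still on treatment", and concludes: "In this case, the Minimax design will be replaced by a simple enrollment of 21 patients". ORR stays the primary endpoint. No new alpha, power or cutoff is given for the single-stage trial.

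**The concern.** There are two separate faults.

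First, two current sections describe different designs. Section 1.6 is a numbered body section that sets the design from Amendment #3 onward, not a log of superseded text. The outdated statement is the one left in the statistical section. A final report built on 14.2 would present the result as coming from a Simon design whose continuation condition was in fact not met.

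Second, the 80% power does not belong to a 4-of-21 rule. This was already so before the amendment and was not caused by it. A reader of 14.2 would take the risk of missing a true 20% ORR to be 20%, when it is 37%. The rule and the stated alpha can also give opposite answers: 3 responders of 21 is significant at 0.1 but fails the cutoff of 4.

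Section 13.0 places any power analysis described in the protocol, along with early stopping rules, in the semi-annual report to the QASMC, so the wrong power could reach the oversight committee as well.

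**Working it through.** **Inputs.** From 14.2: p0 = 0.05, p1 = 0.20, N = 21, one-sided alpha 0.1, power 80%, success at 4 or more. From 1.6.1: first stage of 12, continue with 1 or more responses, then 9 more, 4 responders in total; observed 0/12. All calculations are exact binomial and assume 21 evaluable patients.

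**Reproducing the 80%.** A search over all two-stage designs for 5% versus 20%, with alpha at most 0.10 and power at least 0.80, gives a smallest total of 21. Among designs of that size, the lowest expected sample size under the null is 16.1, with 12 patients in the first stage, stopping at 0 responses, and success at **3** or more. Its alpha is 0.0804 and its power 0.8033. These are the protocol's stage sizes, continuation rule and power, but with a different cutoff.

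**The rule as written, single stage.** P(X ≥ 4) = 1 − [P(0) + P(1) + P(2) + P(3)] with X ~ Bin(21, p):

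- p = 0.05: 1 − (0.3406 + 0.3764 + 0.1981 + 0.0660) = 0.0189
- p = 0.20: 1 − (0.0092 + 0.0484 + 0.1211 + 0.1917) = 0.6296

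**The rule as written, two stages.** Subtract the paths that begin with 0/12, that is P(0 of 12) × P(4 or more of 9):

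- p = 0.05: 0.01888 − 0.5404 × 0.00064 = 0.0185
- p = 0.20: 0.6296 − 0.0687 × 0.0856 = 0.6237

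| Design | Cutoff | Alpha (ORR 5%) | Power (ORR 20%) |
|---|---|---|---|
| Stated in 14.2 | 4 or more | 0.1 | 80% |
| Two-stage 12 + 9 | 4 or more | 0.0185 | 62.4% |
| Single stage, 21 | 4 or more | 0.0189 | 63.0% |
| Two-stage 12 + 9 | 3 or more | 0.0804 | 80.3% |
| Single stage, 21 | 3 or more | 0.0849 | 82.1% |

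With a cutoff of 4, 21 patients in a single stage reach 80% power only at a true ORR of 24.7%.

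**A final result of 3/21.** The one-sided p-value is P(X ≥ 3 | 0.05) = 0.0849, below 0.1. The exact one-sided 90% lower limit is 5.4%, which excludes the 5% null. The cutoff of 4 still calls the trial negative.

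**Where the trial stood after 0/12.** If none of the 12 responds later, success needs 4 or more of the last 9:

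- ORR 20%: 0.0856
- ORR 30%: 0.2703
- ORR 5%: 0.0006

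Three patients were still on treatment, and Section 12.4.3 counts best response up to progression, so late responses were possible. At ORR 20%, one late response raises the chance to P(X ≥ 3 of 9) = 0.2618, and two raise it to P(X ≥ 2 of 9) = 0.5638.

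**Upper limit from 0/12.** The exact one-sided limits are 1 − 0.1^(1/12) = 17.5% at 90% and 1 − 0.05^(1/12) = 22.1% at 95%. An ORR of 20% is therefore excluded at the 90% level but not at 95%. This treats all 12 outcomes as final.

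**The case against.** The strongest reply is that the arithmetic shows a conflict between the power sentence and the cutoff sentence, and does not show which is wrong. Twenty-one patients do give 80% power at alpha 0.1 with a cutoff of 3, so the 4 may be an off-by-one slip that the fix would make permanent. Also, 1.6.1 gives the 4 only while describing the two-stage design, and attaches no cutoff to the simple enrollment of 21.

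Both observations are fair. That the 4 is a slip is plausible, but it is an inference: the documents do not report the design's boundary values. Four is the only cutoff either section contains, and lowering it after 0/12 would be a post hoc change. Keeping 4 with its true error rates, and disclosing that 80% matched 3, is the course that needs no guess about intent.

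It can also be said that the harm is limited. The rule is stricter than the stated alpha; dropping the interim stop moves alpha only from 0.0185 to 0.0189; the study is a single-institution pilot; 14.3 reports the ORR with an interval in any case; and the QASMC report must also summarize substantive amendments, so the committee should hear of the change of design. All of this stands: false positives are not inflated, and the override is openly disclosed in 1.6.1. It does not make the stated power correct or bring 14.2 into line with the amended design.

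**Conclusion.** The concern holds on both counts. Section 14.2 names a design that 1.6.1 has replaced, and no section gives operating characteristics for the trial now being run. The stated 80% is 17 points too high for the stated rule: exact power is 63.0% single-stage and 62.4% two-stage, with alpha near 0.019 rather than 0.1. The amendment did not cause the shortfall; the cutoff of 4 did.

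The design figures assume 21 evaluable patients. Section 5.2 allows some patients to be non-evaluable for response, and no allowance for that is stated or applied here. The 8.6% chance of success is conditional on 0/12 with no late response and a true ORR of 20%. It should not be read as the power of the design.

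**What to change.** Rewrite Section 14.2 as follows:

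1. Remove the two-stage MiniMax statement and describe a single-stage design with 21 patients from Amendment #3.
2. State that the condition in 1.6.1 (at least one response in the first 12 patients) was not met and was overridden by amendment, and that the final report will say so.
3. Keep the cutoff of 4 or more. Replace the 80% power and alpha of 0.1 with the exact values: alpha 0.019 at ORR 5% and power 63.0% at ORR 20%. Disclose that the 80% matched a cutoff of 3 or more, which is not used. Any change of cutoff now would have to be made in both sections and labelled post hoc.
4. Optionally, beside these figures and not in their place, give the chance of reaching 4 responders after 0/12 (8.6% at ORR 20%), labelled as conditional and as assuming no late responders.

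Only the wording of 14.2 changes. The sample size, the cutoff and Section 1.6.1 stay as they are. The cost is a less favourable stated power, 63.0% instead of 80%.

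### Section 14.2 claims 80% power for 21 patients, but its success rule of 4 or more responders has only about 63% power at a true ORR of 20%

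*Combined protocol and SAP*

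**What the plan says.** Section 14.2 sets the hypotheses ("Assuming a null hypothesis of ORR less than 5% in this setting", with 20% or higher as the rate of interest). It gives the operating characteristics as "A total number of 21 patients allows an 80% power at 1-sided alpha of 0.1 to detect the expected difference" and the decision rule as "If 4 or more responders are observed at the end of the trial, we would conclude that there is preliminary evidence for efficacy". It names the design as a Simon "two-stage MiniMax design. We plan to enroll twenty-one (21) advanced-stage NSCLC patients".

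Section 1.6.1 (Amendment 3) describes the stages: 12 patients, then 9 more if at least one responds, "with a total of 4 responders indicating the preliminary evidence of efficacy". It reports no responses in the first 12 and then says that "the Minimax design will be replaced by a simple enrollment of 21 patients". It gives no new power or alpha for the amended design, so the 80% in 14.2 is the only power figure a reader has.

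**The concern.** Sample size, null rate, target rate, boundary, power and alpha are all stated, and for a binomial endpoint the first four fix the last two. Here they do not match.

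ORR is the sole primary objective, and this is the only efficacy decision rule. A reader who trusts the 80% would take fewer than 4 responders as carrying a 20% risk of overlooking a treatment with a true ORR of 20%. If the power is lower, a negative result says less than the plan claims. The outcome most affected is 3 of 21: it misses the written threshold but would meet the one that fits the stated power and alpha.

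A related point is that 14.2 still names the minimax design that 1.6.1 says was replaced, so 14.2 does not say which design its power describes.

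**Working it through.** **Inputs.** From 14.2: n = 21, null ORR p0 = 0.05, target ORR p1 = 0.20, success at 4 or more, claimed power 0.80, one-sided alpha 0.10. From 1.6.1: first stage of 12, stop if there are no responses, second stage of 9; under Amendment 3, a single enrollment of 21.

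**Step 1: what reproduces the stated 80%.** I searched all two-stage designs with alpha at most 0.10 and power at least 0.80 at these rates. The smallest total is 21. At that size the lowest expected sample size under the null is 12 + 9 × (1 − 0.95^12) = 12 + 9 × 0.4596 = 16.1. It belongs to the design that stops at 0 of 12 and rejects the treatment at 2 or fewer of 21, so success is **3** or more. The plan's stage sizes and total are those of this design. Only the 4 differs.

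**Step 2: single enrollment.** With X ~ Bin(21, p), the probabilities of 0, 1, 2 and 3 responders are:

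| p | X = 0 | X = 1 | X = 2 | X = 3 |
|---|---|---|---|---|
| 0.20 | 0.0092 | 0.0484 | 0.1211 | 0.1917 |
| 0.05 | 0.3406 | 0.3764 | 0.1981 | 0.0660 |

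- Success at 4 or more: power = 1 − 0.3704 = 0.6296; alpha = 1 − 0.9811 = 0.0189.
- Success at 3 or more: power = 1 − 0.1787 = 0.8213; alpha = 1 − 0.9151 = 0.0849.

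**Step 3: original two-stage design.** Stopping at 0 of 12 removes only the paths with no response in the first 12 and enough in the last 9. Power is therefore P(X ≥ r) − P(0 of 12) × P(at least r of 9).

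- r = 4, p = 0.20: 0.6296 − 0.0687 × 0.0856 = 0.6237.
- r = 4, p = 0.05: 0.0189 − 0.5404 × 0.0006 = 0.0185.
- r = 3, p = 0.20: 0.8213 − 0.0687 × 0.2618 = 0.8033.
- r = 3, p = 0.05: 0.0849 − 0.5404 × 0.0084 = 0.0804.

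| Success rule | Design | Power at 20% | Type I error at 5% |
|---|---|---|---|
| 4 or more | two-stage | 62.4% | 0.0185 |
| 4 or more | single | 63.0% | 0.0189 |
| 3 or more | two-stage | 80.3% | 0.0804 |
| 3 or more | single | 82.1% | 0.0849 |

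**Step 4: can another reading rescue 80%?** No other first-stage split can, because a futility stop can only remove successes: 63.0% is the ceiling for 4 or more of 21. A one-sample normal approximation comes near (79.5%), but only at alpha 0.05, not the stated 0.10, and it does not describe the 4-responder rule.

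**Step 5: what the written rule does support.** With 4 or more of 21, power reaches 80% at a true ORR of 24.7% (single) or 24.9% (two-stage). At an ORR of 20%, a boundary of 4 first exceeds 80% power at 27 patients (81.8%, alpha 0.044).

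**Step 6: after 0 of 12.** The figures above are design-stage values. Section 1.6.1 reports that "3 out of the 12 patients (25%) are still on treatment with progression-free survival higher than 6 months", and section 12.4.3 says "The best overall response is the best response recorded from the start of the treatment until disease progression/recurrence", so a late response in the first 12 could still count. At an ORR of 20% in the last 9 patients, the chance of reaching 4 is:

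- no late response: P(at least 4 of 9) = 8.6%
- one: P(at least 3 of 9) = 26.2%
- two: P(at least 2 of 9) = 56.4%
- three: P(at least 1 of 9) = 86.6%

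The documents give no basis for weighting these cases.

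**The case against.** The strongest objection is that the power may be right and the boundary wrong. Everything except the 4 fits the minimax design with success at 3, so rewriting the power could adjust a correct figure to suit a misprinted rule. That is a reason to look at the original design record. It is not a reason to assume 3: both sections that give a boundary give 4, and lowering it on inference after 0 of 12 would be a data-informed relaxation. The visible text also postdates that result, so it does not show when 4 was set.

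A second objection is that the harm is limited. This is a small pilot with mainly descriptive analysis, the false-positive risk is well under its limit, and section 14.3 adds a one-sided 90% confidence interval for ORR. If that interval is an exact lower bound (neither direction nor method is stated), 3 of 21 gives 5.4%, just above the null. This does soften reliance on the 4-responder rule. It does not correct the power, and it would put an interval excluding 5% beside a result that misses the written threshold.

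Third, 63% no longer describes the trial's prospects after 0 of 12. That is true, so any restated figure must be labelled as unconditional. The outdated design name is a separate documentation point; it moves power by only 0.6 points.

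**Conclusion.** The concern holds, with high confidence, and should be fixed. For the written rule, power at an ORR of 20% is 62.4% (two-stage) or 63.0% (single enrollment), about 17 points below the stated 80%. The miss risk is 37.6% or 37.0% instead of 20%. Type I error is about 0.019, inside the 0.10 limit, so the error is one of lost power and not of false positives.

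The result rests only on stated inputs and exact binomial calculation, with all 21 patients counted in the denominator. That the intended boundary was 3 is an inference. It matters at exactly 3 of 21, where the exact one-sided p-value is 0.085.

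**What to change.** 1. **Check the original design record for the boundary, and keep 4 as the rule meanwhile.** Change it to 3, in both 14.2 and 1.6.1, only if the record shows that 3 was intended, and disclose that the change was made with 0 of 12 known.
2. **If 4 stands, replace the power sentence in 14.2**, for example: *With success defined as 4 or more responders, 21 patients give about 63% power at an ORR of 20% (62% under the original two-stage design) and a one-sided type I error of about 0.02 at an ORR of 5% (exact binomial, not conditional on the first 12 results).*
3. **Reconcile the design description in 14.2 with 1.6.1**, for example: *The trial was first planned as a Simon two-stage minimax design; Amendment 3 changed it to one enrollment of 21 after the first 12 patients had no responses.*
4. **Optional:** if a chance of success after 0 of 12 is reported, state the assumed ORR in the last 9 patients and the assumed number of late responses in the first 12.

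The cost is two sentences in 14.2 and a look at the design file, with no extra patients and no change to the decision rule. The stated power becomes less favourable. A move to 3, even if documented, would be open to challenge because it follows the interim result.
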